#### 2.3.3 Secondary outcome analyses

- Change in pre-intention factors of Unified Theory of Behavior Change at baseline and approximately 4 months later.

The dependent variable will be the change in adolescent and parent self-report of pre-intention factors. Items were reported using a 5- or 7-point scale, depending on the item, which was then re-scaled to a 5-point scale for ease of interpretation. Differences in change score between intervention and control groups on this outcome will be evaluated using a Paired t-test.

- Change in intention to take/give ADHD medicine regularly at baseline and approximately 4 months later.

The dependent variable will be the change in the intention to take/give ADHD medicine. Items were reported using a 7-point scale, which were then re-scaled to be on a 5-point scale for ease of interpretation. Differences in change score between intervention and control groups on this outcome will be evaluated using a Paired t-test.

- Change in adolescent-report of medication barriers at baseline and approximately 4 months later.

The dependent variable will be the change in adolescent-report of medication barriers. Items were reverse coded so that higher scores mean less barriers. Differences in change score between intervention and control groups on this outcome will be evaluated using a Paired t-test.

- Change in parent-report of medication barriers at baseline and approximately 4 months later.

The dependent variable will be the change in parent-report of medication barriers. Items were reverse coded so that higher scores mean less barriers. Differences in change score between intervention and control groups on this outcome will be evaluated using a Paired t-test.

- Change in medication diversion at baseline and approximately 4 months later.

The dependent variable will be the change in medication diversion. Differences in change score between intervention and control groups on this outcome will be evaluated using a Paired t-test.

- Change in Decision Making Involvement Scale at baseline and approximately 4 months later.

The dependent variable will be the change in parent and adolescent-report of the Decision Making Involvement Scale subscale scores. Differences in change subscale score between intervention and control groups on this outcome will be evaluated using a Paired t-test.

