15. Client Satisfaction Questionnaire (CSQ) (Attkisson et al. 1982) is an 8-item unidimensional measure of client satisfaction with services. Psychometric properties, operating characteristics, and coefficient alpha (.93) are very strong for this measure which we will collect from adolescents and parents.
16. Decision Making Involvement Scale (DMIS) (Miller et al., 2012): is a 30-item scale to measure adolescent involvement in a decision. The five subscales are: “Child Seek” (child asks for an opinion or information from parent), “Child Express” (child expresses an opinion or information to parent), “Parent Seek” (parent expresses advice or opinion to child), “Parent Express” (parent expresses advice or opinion to child), and

“Joint/Options” (negotiation or brainstorming between parent and child). We will collect this measure from adolescents and parents.

DATA ANALYSIS

Hypothesis testing:

Each hypothesis examines part of the mechanism underpinning intervention impact on medication continuity.

Hypothesis #1: *Adolescents will use greater than 80% of relevant intervention components.* For each subject in the intervention group, we will calculate the proportion of **recommended** intervention components that were utilized by the subject during the study. The mean and 95% confidence interval (CI) will be computed to give a range estimate of the fidelity measure. To evaluate our hypothesis, we will utilize the computed CI to determine if 80% or greater is a plausible value, such that if the CI includes a value of 80% or greater we will reject the null hypothesis. We will also examine the temporal distribution of use for each of the recommended components.

Hypothesis #2: *Use of the intervention components will be related to improvements in the targeted UTBC factors.* Using a generalized linear model, we will test whether the intervention addressed the UTBC factors (i.e., pre-intention factor scales and ABMS/PBMS total and subscale scores). Model predictors will include a fixed effect indicator of time point (baseline or end of study). A significant effect of time point in the expected direction would indicate UTBC factor improvement.

Hypothesis #3: *Medication continuity will be higher in the intervention group compared to the control group.* We will compare the percentage of days covered with medicine using a two-sample t-test.

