Hypothesis #4: *Pre-post changes in UTBC factors will be related to increases in medication continuity.* We will calculate the change score for each relevant UTBC factor (end of study minus baseline) and the change score for medication continuity (percentage of days covered at end of study minus percentage of days covered in the 12 months prior to study). We will model the association between change in UTBC factor scores (independent variable) with change in medication continuity (dependent variable) using generalized linear mixed model. A significant effect of change in UTBC factor scores (beta coefficient) in the expected direction would indicate changes in UTBC factor scores were associated with medication continuity improvement.

Exploratory analyses:

We will conduct descriptive analyses to characterize rates of diversion at baseline and at the end of study using a McNemar's test to see if rates differ. We will summarize responses to the client satisfaction questionnaire descriptively as this may facilitate future dissemination.

Power and Sample Size:

The study would require a sample size of 18 for each group (i.e. a total sample size of 36), to achieve a power of 80% and a level of significance of .05 (two sided), to detect a difference in means between the intervention and the control groups of 15.7% (i.e. 66.2% vs. 50.5%) on the percentage of days covered with medicine assuming a pooled standard deviation of 16.5. Due to the low intra-class correlations observed in previous studies of ADHD medication continuity (ICC = 0; [name] et al. 2018), the analyses will not account for the nesting of patients within physicians. We will recruit 44 patients to ensure that 36 are retained at the end of the study. A retention rate of 80% (36/44) is conservative in light of the 12-month retention rate of 92% achieved by [name] in his current trial. We will use a stratified blocked randomization procedure to ensure baseline medication continuity is evenly distributed in both arms.

Scientific Rigor:

The RCT is a rigorous design to test efficacy of our intervention. We will explicitly address whether the intervention engages the mechanism underlying medication continuity and therefore warrants further testing in a future larger trial. Our preliminary data strongly supports the importance of the problem, intervention targets identified, and the feasibility of the approach in our hands.

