Official Title of the study: **Randomized Controlled Trial of Web Based Tools to Improve Medication Continuity in Adolescents With ADHD**

NCT number: **NCT04386096**

Document name: **Statistical Analysis Plan**

Date of the document: **12/15/2021**

The results of the Web Based Tools study will be assessed as described in this document. This statistical analysis plan begins with an overview of the key components of the study, including its design, objectives, and outcomes measures. This is followed by a detailed description of the statistical analyses that will be utilized to address study hypotheses.

**1. Overview of study:** This study used a parallel group randomized control trial to test whether an intervention engages the proposed mechanism underlying medication continuity and improves outcomes. Adolescents and their parents that agreed to participate in the study were randomized to receive either the intervention (MeHealth for ADHD software with medication continuity tools) or the control group (MeHealth for ADHD software with no medication continuity tools). We used a stratified randomization procedure to ensure that the intervention and control groups were balanced with respect to the number of days covered with ADHD stimulant medication in the past year based on dispensing data. We planned to enroll a total of 44 adolescents aged 11-15 with ADHD with poor medication continuity from Cincinnati Children's Pediatric Primary Care Clinic (PPCC) in order to retain  $\geq 36$  subjects needed based on our sample size calculation.

**1.1 Study Objective:** Test a multi-component intervention that systematically identifies and targets aspects of the Unified Theory of Behavior Change (UTBC) model most relevant for each adolescent with poor ADHD medication continuity.

Working hypothesis 1: compared to the control group, the intervention group will have greater medication continuity as measured by number of days covered with medicine at the end of the study.

Working hypothesis 2: compared to the control group, the intervention group will have improved outcomes as measured by change in the Unified Theory of Behavior Change factors.

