#### 2.3.2 Primary outcome analysis

*Primary outcome:* Medication continuity as measured by proportion of days covered with medicine during the 4-month trial.

- Number of days covered with medicine is calculated from audit of prescriptions dispensed.

For the primary outcome, the dependent variable will be a proportion of the number of days covered with ADHD medicine during the 4-month trial. Differences between intervention and control groups on this outcome will be evaluated using a two-sample t-test or Wilcoxon rank sum test.

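### SAP 2.3.3 names a paired t-test for all six between-arm secondary comparisons, so no valid test of Working hypothesis 2 is specified

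*SAP*

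**What the plan says.** SAP 1 describes the design: "This study used a parallel group randomized control trial to test whether an intervention engages the proposed mechanism underlying medication continuity and improves outcomes". The protocol, under Power and Sample Size, adds: "We will use a stratified blocked randomization procedure to ensure baseline medication continuity is evenly distributed in both arms". Neither document describes matching individuals across arms.

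Working hypothesis 2 in SAP 1.1 is a comparison with control: "compared to the control group, the intervention group will have improved outcomes as measured by change in the Unified Theory of Behavior Change factors".

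SAP 2.3.3 covers six secondary outcomes: pre-intention factors, intention, adolescent-reported barriers, parent-reported barriers, diversion and the Decision Making Involvement Scale (DMIS). Five bullets carry the sentence "Differences in change score between intervention and control groups on this outcome will be evaluated using a Paired t-test". The DMIS bullet differs by one word: "Differences in change subscale score between intervention and control groups on this outcome will be evaluated using a Paired t-test".

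For the same kind of contrast on the primary outcome, SAP 2.3.2 says: "Differences between intervention and control groups on this outcome will be evaluated using a two-sample t-test or Wilcoxon rank sum test".

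**The concern.** A paired t-test needs a one-to-one link between the two sets of values. Within a participant, baseline and end of study are linked, but taking the change score uses up that link. Between arms there is none. An analyst who follows the words must either link unrelated adolescents across arms or fall back on a pre/post test inside each arm.

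The second route matters more. It asks whether an arm changed, not whether the arms changed by different amounts. Anything that moves both arms, such as the start of the school year, answering the questionnaires a second time or the attention of being in a study, could then be reported as an effect of the tools, and the protection of randomisation is lost. Whether the intervention engages its proposed mechanism is a stated purpose of the trial, and the protocol (Scientific Rigor) ties the case for a larger trial to that question.

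**Working it through.** **1. Is there a valid arm comparison of the UTBC factors anywhere else?**

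| Place | Analysis | Arm term? |
|---|---|---|
| Protocol, Hypothesis #2 | Generalized linear model; "Model predictors will include a fixed effect indicator of time point (baseline or end of study"; a significant time effect counts as improvement | No |
| Protocol, Hypothesis #4 | Change in UTBC factors against change in continuity | No |
| Protocol, Exploratory analyses (diversion) | Baseline against end of study, "using a McNemar's test to see if rates differ" | No |
| SAP 2.3.1 | Adjustment for baseline characteristics that differ widely; no model named, and a t-test takes no covariates | None specified |
| SAP 2.3.3 | Arm contrast stated, paired t-test named | Contrast yes, test no |

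No section supplies one.

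**2. The plan's own sample size.** Inputs from the protocol, Power and Sample Size: difference 66.2 − 50.5 = 15.7, SD 16.5, two-sided alpha 0.05, power 80%. Normal approximation: n = 2 × (16.5/15.7)² × (1.960 + 0.842)² = 17.3, so 18 per arm, as stated. With the t distribution (df 34), power at 18 per arm is 79.2%. This figure concerns the primary outcome only; the documents give no power for any secondary outcome. I use 18 per arm below.

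**3. Reading A: pair across arms.** With unequal numbers the test cannot run. Unequal numbers are likely: 44 are recruited in order to retain 36, and surveys can be missing. With equal numbers the pairing is arbitrary:
- Degrees of freedom fall from 34 to 17. Power at a standardised difference of 15.7/16.5 = 0.95 falls from 79.2% to 76.7%; at 0.8 it falls from 64.5% to 61.9%. The loss is small.
- The p-value depends on row order. In one simulated data set of 18 against 18, the independent-samples test gave p = 0.019, while 10,000 random pairings of the same values gave p from 0.0015 to 0.065. This is one illustration, not an estimate of typical size.

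**4. Reading B: pre/post test within each arm, n = 18.** Let both arms change by the same amount δ, in SDs of the change score, so there is no intervention effect. The test statistic is noncentral t with df 17, noncentrality δ√18 and critical value 2.110. Let p be the probability of significance in one arm. The arms are independent, so the chance of significance in intervention but not in control is p(1 − p).

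| δ (assumed) | Noncentrality | Intervention arm significant, p | Intervention significant, control not, p(1 − p) |
|---|---|---|---|
| 0 | 0 | 5.0% | 4.8% |
| 0.1 | 0.42 | 6.9% | 6.4% |
| 0.2 | 0.85 | 12.6% | 11.0% |
| 0.3 | 1.27 | 22.5% | 17.4% |
| 0.5 | 2.12 | 51.6% | 25.0% |
| 0.8 | 3.39 | 89.2% | 9.6% |

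The last column drops at 0.8 because both arms are then usually significant. The documents give no value for δ; the range is an assumption.

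**5. After correction.** An independent two-sample t-test on change scores with 18 per arm (df 34) has 80% power for a difference of 0.96 SD of the change score; with 22 per arm, 0.86 SD. The sample size does not change, because it rests on the primary outcome, which already has an independent-samples test.

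**The case against.** The strongest reply is that this is a drafting slip for a two-sample test. The SAP defines the dependent variable as a change, states the contrast as one between arms, and uses an independent-samples test in 2.3.2. On that view neither reading A nor reading B would ever be carried out. The explanation is plausible, but it does not repair the text. The same term appears six times, and the protocol's Hypothesis #2 is itself a pre/post analysis, so a within-arm test is a realistic way to carry out the plan. The SAP is dated 12/15/2021 and gives a study end date of 5/24/21, so an unresolved choice of test could be settled with data in hand.

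Several narrower points stand:
- The reading B percentages are the power of a within-arm test against a different null hypothesis. They show how often shared change would be mistaken for an effect, and they depend on δ; at 0.1 SD they are close to nominal.
- Regression to the mean is a weaker source of shared change here than it first appears, because entry selects on days covered, not on UTBC scores.
- Under reading A, a pairing fixed in advance keeps the type I error at 5%. The faults are arbitrariness and failure with unequal arms.
- Protocol Hypotheses #2 and #4 bear on mechanism, though neither compares arms.
- Diversion and the DMIS share the error but are not clearly UTBC factors, so they bear less directly on Working hypothesis 2.
- A two-sample test alone cures the defect; ANCOVA goes further than the minimum.

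**Conclusion.** The concern holds. All six secondary comparisons in SAP 2.3.3 name a test that does not fit the contrast they state, and no other section gives a valid between-arm test of the UTBC factors. Working hypothesis 2 is stated properly but has no valid test specified for it.

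The size of the harm depends on how the text is carried out. As within-arm tests, the chance of a spurious intervention-arm finding rises from 5% to 22.5% at a shared change of 0.3 SD and to 51.6% at 0.5 SD. This assumes 18 per arm, approximately normal change scores and an equal change in both arms. As cross-arm pairing, the loss of power is small but the p-value is arbitrary. The correction must be made before the secondary results are interpreted. The primary analysis and the sample size are untouched.

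**What to change.** In all six bullets of SAP 2.3.3, replace the paired t-test with a comparison of independent arms:

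- **Minimum:** a two-sample t-test on change scores, or the Wilcoxon rank sum test that 2.3.2 already allows. State in advance which applies when.
- **Preferred:** ANCOVA of the end-of-study score on arm and the baseline score of the same scale. This also provides a model that can take the covariate adjustment promised in SAP 2.3.1.
- Report the arm difference with its 95% confidence interval for every outcome.
- For diversion, which is a count of occasions and may be mostly zeros (the documents give no rate), compare arms with a permutation or exact test.
- Keep paired results within each arm as description only, with no inference about the intervention drawn from them.

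Because the SAP post-dates the study end, date the change and state whether results by arm had been seen. If they had, report the two-sample test as the direct correction and ANCOVA as a supporting analysis.

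The cost is SAP wording and a different SAS procedure. No new data are needed, since the baseline scores are already part of the plan.

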#### 2.3.4 Intervention Fidelity measures

##### *Intervention group only*

The following will be summarized as mean and full range:

- Proportion of intervention components completed relative to the component that were recommended by the portal based on adolescent/parent responses to the assessment battery.
